18.5 Appendix 5 – NCI-CTC Version 4.03 (CTCAE v4.03)

18.6 Appendix 6 – Declaration of Helsinki, Republic of South Africa, October 1996

18.7 Appendix 7 – Summary of Changes

The following table provides a summary of changes to the Clinical Study Protocol version 5.0 (02-SEP-2020), which are included in version 4.0 (26-NOV-2018). Minor editorial changes have also been made but are not included in this summary table.

Summary of changes to previous protocol version

Section number	Section title	Version 4.0	Version 5.0 (Changes / additions in bold italic and deletions as strikethrough)	Type of change and justification for changes
	Synopsis page 7 Inclusion Criteria	11. d. INR 1.4 and PTT < 40 seconds during the last 7 days before therapy	11. d. INR < 1.4 and PTT < 40 seconds during the last 7 days before therapy	Change: non- substantial Justification: Alignment with section 4.2
	Synopsis page 12 Inclusion Criteria	Study plan FPI Q3/2017 LPI after approx. 18 month LPO after approx. 22 month EoS (after 24 month FU of LPO) after approx. 46 month	Study plan FPI Q2/2018 LPI after approx. 36 month (Q2/2021) LPO after approx. 40 month (Q4/2021) EoS (after 24 month FU of LPO) after approx. 64 month (Q4/2023)	Change: non-substantial Justification: Adjustment, trail recruitment
3.7 Study	Inclusion Criteria	Study plan FPI Q3/2017	Study plan FPI Q2/2018	Change: non-substantial Justification:

Page 102/102

Section number	Section title	Version 4.0	Version 5.0 (Changes / additions in bold italic and deletions as strikethrough)	Type of change and justification for changes
Duration	page 38 / 39	LPI after approx. 18 month LPO after approx. 22 month EoS (after 24 month FU of LPO) after approx. 46 month	LPI after approx. 36 month (Q2/2021) LPO after approx. 40 month (Q4/2021) EoS (after 24 month FU of LPO) after approx. 64 month (Q4/2023)	Adjustment, trail recruitment

| | 7.1.1 | Overall Study Information | 18 |
| | 7.1.2 | Baseline Evaluation | 18 |
| | 7.1.3 | Efficacy Analysis | 18 |
| | 7.1.4 | Safety Analysis | 19 |
| | 7.2 | List of Data Listings | 20 |
| | 7.2.1 | Overall Study Information | 20 |
| | 7.2.2 | Baseline Data | 20 |
| | 7.2.3 | Efficacy Data | 21 |
| | 7.2.4 | Safety Data | 22 |

List of Abbreviations

| AE | Adverse event |
|------------|--|
| CEA | Carcinoembryonic antigen |
| CI | Confidence interval |
| CSP | Clinical study plan |
| CTCAE | Common terminology criteria for adverse events |
| Cyfra 21-1 | Cytokeratin-fragment 21-1 |
| DFS | Disease-free survival |
| DLCO | Diffusion capacity of lung for CO |
| DRM | Data review meeting |
| ECG | Electrocardiogram |
| ECOG | Eastern Cooperative Oncology Group |
| eCRF | Electronic case report form |
| FEV | Forced expiratory volume |
| FU | Follow-up |
| IMP | Investigational medicinal product |
| ІТТ | Intent-to-treat |
| LD | Least diameter |
| NCI | National Cancer Institute |
| NSCLC | Non-small cell lung cancer |
| OA | Overall |
| OS | Overall survival |
| PP | Per-protocol |
| PT | Preferred term |
| RECIST | Response Evaluation Criteria in Solid Tumors |
| SAE | Serious adverse event |
| SAP | Statistical analysis plan |
| SB | Single breath method |
| SD | Standard deviation |
| SOC | System organ class |
| SUV | Standardized uptake value |
| TL | Target lesion |
| TLFs | Tables, listings and figures |
| VA | Alveolar volume |
| VC | Vital capacity |

1. OVERVIEW

1.1 Study Objectives

- 1.1.1 Primary Objective
 - To assess feasibility and safety of a neoadjuvant application of pembrolizumab.
 - To assess antitumor activity of pembrolizumab with regard to clinical and pathologic tumor response.

1.1.2 Secondary Objectives

To assess the impact of neoadjuvant pembrolizumab on patient disease free and overall survival.

1.1.3 Exploratory Objectives

To explore potential predictive biomarkers for Pembrolizumab efficacy by immune cell and cytokine analysis:

- Inflammatory infiltrates in and around the resected tumor
- tumor tissue and serum cytokine profiles
- Hypothesis generation on potential biomarkers predicting efficacy of pembrolizumab using multi-OMICS analysis

1.2 Study Design

The study is designed as an open-label, single arm, prospective, monocenter, phase II study of pembrolizumab in a neoadjuvant setting in patients with non-small cell lung cancer of Stage II/IIIA suitable for curative intent surgery.

1.3 Endpoints

- 1.3.1 Primary Endpoint
 - Frequency and severity of AEs including peri- and post-operative complications (grade 2-4 AEs according to NCI-CTCAE V4.03)
 - o number of patients treated in compliance with protocol
 - Tumor response evaluation

clinical response parameters:

- o response rates (Δ tumor size / lymph node size), according to RECIST 1.1 criteria
- Δ PET-activity (standardized uptake value [SUV]) (analysis of this end point is not covered in this SAP)
 Pathologic response parameters:
- Pathologic regression grading according to Junker criteria (see Appendix 3 of CSP)
- 1.3.2 Secondary Endpoints
 - disease free survival
 - overall survival

1.3.3 Exploratory Endpoints

Following exploratory endpoints were defined for this study, but will not be covered by this SAP:

- prognostic value of tumor shrinkage •
- prognostic value of inflammatory infiltrates in and around the resected tumor •
- serum- and tumor tissue cytokine concentrations •
- multi-OMICS tissue analysis approach for markers and mechanisms

1.4 Sample Size Calculation

A phase II approach will be used to generate preliminary hypothesis generating data. No formal sample size estimation has been performed. The scope is to gather information on feasibility, safety and efficacy. Target sample size is N=30.

The rationale for the sample size of this trial is based on ethical, clinical as well as scientific considerations. The neo-adjuvant treatment approach with an immune check-point inhibitor is highly experimental with only limited data on safety and feasibility available. Therefore, only a small number of patients should be subjected to this experimental treatment. Nevertheless, the sample size should allow the generation of statistically meaningful evidence for feasibility and safety to permit the decision to further develop this treatment approach.

With a sample size of N=30 and assuming that the number of events follows a binomial distribution B(30,p), events with an incidence rate p > 9.5% will be observed at least once with a 95% probability. This observation limit will exclude individual pembrolizumab related SAEs but covers most of the historical reference events/rates of the primary endpoints in this trial as well as the early stopping rule.

1.5 Schedule of Study Assessments

| Study Phase | Screening | Treatment phase | | Pre- Surgery | Dis-charge | End of treatment | Follow-up |
|---|------------------|-------------------|-------------------|-----------------|------------|---------------------|-------------------|
| Visit | SCR | V1 | V2 | PS | D | EOT | FU1 – FUx |
| Time windows | Day - 28 to 0 | Day 1 | Day 21 +/- 3 days | Day 43-50 | Day 60-74 | 6 wks. after | every 3 months |
| Informed consent | X | | | | | Surgery | |
| Demographics | Х | | | | | | |
| (age, gender, race) | | | | | | | |
| Tumor diagnosis | Х | | | | | | |
| Cancer history | Х | | | | | | |
| Medical history (incl. smoking status) | Х | | | | | | |
| Previous treatments | X | | | | | | |
| Tumor assessments (PET)-CT, RECIST 1.1 | X | | | х | | | |
| Tumor staging | х | | | | | | |
| (PET-CT, MRI DIalit) Chest X ray | Y | | Y | × | × | Y | |
| Cardiac evaluation | ~ | | ^ | ^ | ^ | ^ | |
| (12-lead ECG) | × | | (X) ¹ | Х | | X | |
| Physical examination ² | Х | | X | Х | X | X | |
| Body weight and height / BSA ³ | X | | X | X | | X | |
| Vital signs | Y | 001 | v | × | V | × | |
| (BP, HR, body temperature) | ^ | (∧)° | ^ | ^ | ^ | ^ | |
| Lung function test | х | | x | x | | х | |
| ECOG status | Y | | ¥ | × | | × | |
| Pregnancy test (if applicable) | × | (X) ⁸ | ^ | ^ | | ^ | |
| Hematology4 | X | (X) ⁸ | X | X | X | × | |
| Coagulation | X | (X) ⁸ | X | X | X | X | |
| Clinical chemistry ⁵ | X | (X) ⁸ | X | X | X | X | |
| tumor marker | X | | | X | ~~~~ | X | |
| TSH ⁶ | X | | X | X | X | X | |
| In- / Exclusion criteria | X | | | | | | |
| Biomarkers (blood sample) | | X | Х | Х | X | Х | |
| Tumor tissue ⁹ | Х | | | | Х | | |
| HR-QoL | Х | | | Х | | Х | |
| Treatment (V1/V2) | | Pembrolizumab 200 | Pembrolizumab 200 | | | | |
| Concomitant medication | Х | | Contin | uously | | 1 | |
| Concomitant procedures | X | | Contin | uously | | | |
| Adverse events X | | Contin | uouslý | | | X7 | |
| Subsequent cancer therapy | | | | | | | Х |
| Survival status | | | | | | | Х |

¹ if clinically indicated. Consult a specialist if clinically abnormal and exclude any immune-related myocarditis.

² Full examination is required at baseline and end of treatment. Focused clinical examination shall prevail throughout the course of treatment.

³ Body height will only be measured at screening.

⁴ Full blood count including blood differential test will be performed at baseline, after start of treatment (V2) and further indicated time points throughout treatment and at end of study.

⁵ Sodium, potassium, calcium, magnesium, phosphate, AST, ALT, PTT/INR, LDH, total bilirubin, creatinine, creatinine clearance, albumin, tumor marker CEA, Cyfra 21-1

⁶ To be done at baseline and 3 weeks after start of treatment (V2) and further indicated time points throughout treatment and at end of study. If rising TSH is detected, a full assessment of fT3 and fT4 shall be performed and signs of hormone depletion shall be monitored clinically.

⁷ Follow-up of ongoing SAEs until resolution or stabilization. Serious adverse events are recorded until 90 days after last dose of IMP or for 6 weeks after surgery if the subject initiated new anticancer therapy (e.g. radiochemotherapy). Pregnancies occurring in a study subject are recorded from time of signed informed consent until 120 days after last dose of IMP.

 $^{8}\,$ Repeat assessment if SCR assessment is older than 7 days.

⁹ Post-op. tumor regression grading.

2. GENERAL CONSIDERATIONS

2.1 Conduct of Analysis

Two analyses will be performed for this study.

- Main analysis will be performed after all patients had their end of treatment, data entry for all visits except the follow-up visits is complete, data were cleaned, a Data Review Meeting was performed and database snapshot has been completed.
- Addendum analysis will be performed after last patient completed the entire study, follow-up data entry and cleaning are complete and database was closed.

Main analysis will summarize all data recorded up to the time of the database snapshot. Addendum analysis will only present data captured during follow-up. This means, the addendum analysis may only include overall survival, end of study details and subsequent cancer therapy. An SAE listing will also be prepared to show possible follow-up information of SAEs ongoing after end of treatment.

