3.3 Follow-up Phase

After treatment discontinuation, follow-up evaluations will be performed every 3 months in order to collect information on relapse, survival status and subsequent cancer treatment until end of study.

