5.2.6 Follow-up

AIO-Studien-gGmbH

After discontinuation of treatment, all patients will be followed-up for survival every 3 months. First visit of the follow-up period will take place 3 months after EOT visit. Follow-up of the individual patient will continue until death or until study is terminated. The following information will be collected during the follow-up:

- Survival data
- Subsequent anti-cancer therapy
- Study drug related adverse events continuing from treatment phase will be followed-up until the event has resolved or stabilized

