5.2.7 End of Study

The final statistical analysis will be performed when the last patient has completed at least 24 months of follow-up or death occurred, whichever comes first.

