8.4.3 Efficacy evaluation

Primary efficacy parameter:

Efficacy of the neoadjuvant treatment approach will be evaluated by radiologic tumor response (RECIST 1.1 assessment of base line and pre-surgery CT/MRI), by changes of standardized maximal uptake values (SUVs) of the primary tumor quantified by PET-scans, as well as a pathologic regression grading of resected tumor material according to Junker (see Appendix 18.3).

Secondary efficacy parameters:

Time-to-event measures (OS, DFS) will be analyzed by means of Kaplan-Meier curves.

Details on the analysis of secondary parameters will be given in the Statistical Analysis Plan.

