5.2 Definitions

- Disease-free survival (DFS) will be defined as the time length from the date of surgery to the date of tumor recurrence or death (tumor recurrence as reported on follow-up pages in the eCRF, death as reported in the end of study page in the eCRF). Patients that had no tumor recurrence and did not die will be censored at the date of last contact when patient was alive (as reported on the end of study page in the eCRF).
- Overall survival (OS) will be calculated as the time length from the date of surgery to the date of death. Patients that did not die will be censored at the date of last contact when patient was alive (as reported on the end of study page in the eCRF).
- For both DFS and OS the following rule will be applied for incomplete dates: The date of surgery is assumed to always be completely known (day, month and year available), otherwise DFS and OS will not be calculated. For the end dates (death, tumor recurrence, last date patient was alive) patients will be secured at the earliest possible date. E.g. if the date of death is "UK/05/2019" then the patient is censored at 01/05/2019 and thus being considered event-free until this date and status is considered unknown after

this date. If this rule results in negative survival time, the patient is not considered for Kaplan-Meier analysis.

• Δ tumor size will be defined as the difference [mm] between "current SUM LD" and "baseline sum LD" on the tumor response assessment page of the eCRF.

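### SAP 2.1 names OS but not DFS for the end-of-follow-up (addendum) analysis, so as written DFS is estimated only at the main snapshot

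*SAP*

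**What the plan says.** **Timing of the two analyses (SAP 2.1).** On the main analysis: "Main analysis will be performed after all patients had their end of treatment, data entry for all visits except the follow-up visits is complete". Cleaning, a Data Review Meeting and a database snapshot also come first. The addendum follows once the last patient has completed the study. Its scope is set by "Addendum analysis will only present data captured during follow-up", and the next sentence spells this out: "This means, the addendum analysis may only include overall survival, end of study details and subsequent cancer therapy". An SAE listing is added. DFS and recurrence are not mentioned.

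**DFS elsewhere in the SAP.** Section 5.2 runs DFS from surgery to recurrence or death, with "tumor recurrence as reported on follow-up pages in the eCRF". It takes deaths and the last-contact-alive date from the end of study page. Section 5.3 asks for rates at, for example, 12, 24 and 36 months. Tables 14.3.3 (PP) and 14.3.11 (ITT) hold the Kaplan-Meier results, Listing 16.2.3.6 the individual DFS and OS times, and Listing 16.2.3.11 the recurrences. None of these is assigned to one analysis or the other.

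**Protocol.** Section 3.3 sets visits every 3 months "in order to collect information on relapse, survival status and subsequent cancer treatment until end of study". Section 5.2.7 says "The final statistical analysis will be performed when the last patient has completed at least 24 months of follow-up or death occurred", and section 8.4.3 says "Time-to-event measures (OS, DFS) will be analyzed by means of Kaplan-Meier curves". Section 5.2.6 is narrower ("all patients will be followed-up for survival every 3 months"), and its list of follow-up items does not include relapse.

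**Declared changes.** SAP 2.14 lists departures from the protocol. Leaving DFS out of the final analysis is not among them.

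**The concern.** A programmer who builds the addendum from the SAP 2.1 list would produce OS tables and no DFS tables. OS would then be estimated on full follow-up. DFS would be estimated once, when the most recently operated patients have only a few months of follow-up. Recurrences recorded later would be in the database and in a follow-up listing, but in no planned DFS estimate.

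The main snapshot is also poorly suited to be the only DFS analysis. It does not require follow-up visits to be entered, yet those pages are the only named source of recurrence. The end of study page, which supplies deaths and censoring dates, would be expected only once a patient has left the study. That some patients would lack this page at the snapshot is an inference, since the eCRF is not among the documents.

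**Working it through.** **Reference figure.** The documents state no DFS event count or DFS maturity, so there is none to reproduce. The protocol's timeline is consistent: LPO at month 40 plus 24 months gives study end at month 64.

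**Inputs from the documents.** N = 30; last patient in at month 36; study end at month 64; end of treatment 6 weeks (1.4 months) after surgery; overall 5-year relapse rate 52% (Protocol 1.3).

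**Assumptions.** Uniform accrual; surgery 2 months after inclusion, so surgery dates are spread over months 2 to 38; all 30 resected; no dropout; all events up to the snapshot captured; 52% used as a stand-in for DFS events, although it is an overall relapse figure and not specific to stage II/IIIA. The last end of treatment is then at 36 + 2 + 1.4 = month 39.4. The delay from there to the snapshot is not given; months 43 to 46 are taken as realistic.

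**Constant hazard.** h = -ln(1 - 0.52)/60 = 0.01223 per month. Follow-up from surgery at calendar month s is uniform on (a, b) = (s - 38, s - 2). Expected events = 30 × [1 - (e^(-ha) - e^(-hb)) / (36h)], with 36h = 0.4404.

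- Month 43: 30 × [1 - (0.9407 - 0.6056)/0.4404] = 7.17
- Month 46: 30 × [1 - (0.9068 - 0.5838)/0.4404] = 8.00
- Month 64: 30 × [1 - (0.7276 - 0.4684)/0.4404] = 12.34

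Share still to come: 1 - 7.17/12.34 = 41.9% and 1 - 8.00/12.34 = 35.2%.

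**Other hazard shapes**, each set to 52% at 60 months. Weibull: F(u) = 1 - exp(-(cu)^k), with c = (-ln 0.48)^(1/k)/60. Mixture-cure with half-life m: F(u) = p(1 - 2^(-u/m)), with p = 0.52/(1 - 2^(-60/m)). Share of events after the snapshot:

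| Shape | Month 39.4 | Month 43 | Month 46 | Events by month 64 |
|---|---|---|---|---|
| Constant hazard | 50% | 42% | 35% | 12.3 |
| Weibull, k = 0.8 | 43% | 35% | 29% | 12.9 |
| Weibull, k = 0.7 | 39% | 32% | 26% | 13.2 |
| Cure, m = 12 months | 32% | 24% | 19% | 14.6 |
| Cure, m = 9 months | 27% | 19% | 14% | 15.0 |

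**Other sensitivities.**
- 5-year rate of 40% to 65%, constant hazard, months 43-46: 33-44%.
- Month-49 snapshot, constant hazard: 8.79 of 12.34, so 29% still to come.
- 24 resected instead of 30: 5.7-6.4 of 9.9 events; the share is unchanged.
- LPO read as the last operation (surgery in months 4 to 40), constant hazard: 48% at the last end of treatment (month 41.4), 42% at month 44, 35% at month 47.

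**Patients at risk**, constant hazard: 30 × P(follow-up ≥ τ) × e^(-hτ).
- τ = 36: month 43, 30 × 5/36 × 0.6438 = 2.7; month 46, 30 × 8/36 × 0.6438 = 4.3; month 64, 30 × 26/36 × 0.6438 = 13.9.
- τ = 24: 30 × 17/36 × 0.7456 = 10.6; 30 × 20/36 × 0.7456 = 12.4; 30 × 1 × 0.7456 = 22.4.

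**Precision.** In 20,000 simulated trials under the constant-hazard assumptions (months 43, 46 and 64), the mean Greenwood standard error was about 11.7, 11.1 and 8.8 points for the 36-month rate and 8.9, 8.6 and 7.8 points for the 24-month rate. The 24-month estimate averaged 0.747, 0.746 and 0.745 against a true 0.746. It is therefore unbiased when the data cut is complete.

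**If the data cut is not complete.** In the extreme case that no follow-up pages are in the snapshot, only events before the end of treatment visit count: 30 × (1 - e^(-0.01223 × 1.4)) = 0.5 events. If instead event-free patients had no DFS time because their end of study page is missing, those left would mostly have events and the curve would be much too low.

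**The case against.** The strongest reply is that this is loose drafting and DFS will be run at study end anyway. The governing sentence covers everything captured during follow-up, and recurrence is such data. Taking deaths and censoring dates from the end of study page presupposes that the study is over. Listing 16.2.3.6 holds OS and DFS together, so re-running it for OS would also output individual DFS times. No passage reserves DFS for the main analysis. All of this stands, and it is why the gap is treated as an omission. A reader might infer from the list that the sponsor has decided to drop DFS from the final analysis, or from Protocol 5.2.6 that relapse is not collected in follow-up. The documents support neither: no such decision is declared, and Protocol 3.3, SAP 5.2 and Listing 16.2.3.11 all include recurrence. But an SAP should not leave a secondary endpoint to inference when its own list names one and omits the other.

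A second reply is that little depends on it. DFS is descriptive, is not tested and drives no decision rule, and the 24-month standard error changes by only about 1 point. This also stands. It limits the severity but does not remove the inconsistency.

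**Conclusion.** The wording gap is certain: DFS is missing from the addendum list, nothing else assigns it there, and the list does not fit Protocol 3.3, 5.2.7 and 8.4.3 or the SAP's own scope sentence. Its effect, if followed literally, rests on assumptions. With a constant or moderately declining hazard and a snapshot between the last end of treatment and month 46, roughly 25-50% of expected DFS events would come after the only planned estimate. The share is about 15-30% if recurrence is strongly front-loaded, and lower again with a later snapshot. It would be tempting to quote 35-42% as the result, but that range needs constant hazard and a month 43-46 snapshot, and the documents give neither.

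The loss is mainly precision, most visible at 36 months (about 3-4 patients at risk against 14), provided all events and contact dates up to the snapshot are captured. A reader might conclude that bias is excluded, or that it is certain. Neither follows: follow-up entry need not be complete at the snapshot, and no date source is named for patients without an end of study page. Severity is modest, and the point is worth fixing because the data are already being collected.

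**What to change.** - **SAP 2.1:** add DFS to the addendum list (Tables 14.3.3 and 14.3.11, Listings 16.2.3.6 and 16.2.3.11), so that it is estimated on full follow-up alongside OS. If DFS is meant to stay out, declare and justify that in SAP 2.14.
- **SAP 5.2, only if DFS or OS is also shown at the main analysis:** label it preliminary, and state that event-free patients without an end of study page are censored at their last recorded contact alive on or before the snapshot. This keeps the existing censoring principle and names a date source.

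Cost: one or two sentences and one re-run of existing tables and listings at the addendum. No new data are needed.

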2.2 Statistical Software and Quality Control

All statistical analyses will be performed using SAS[®] version 9.3 or higher. Tables, figures and data listings will be generated in Microsoft[®] Word[®] as well as PDF[®] format.

Quality control of SAS® programs will include a review of the whole process of result generation:

- Review of all analysis SAS® programs
- Review of SAS® log for errors, warnings and other notes that could indicate mistakes in the programs
- Review of all tables, listings and figures for completeness and correctness

